11.2	Ethical Conduct of the Clinical Study.....	66
11.3	Subject Information and Consent	67
11.4	Protection of Personal Data	67
11.5	Contractual Requirements	68
11.6	Data Collection and Archiving.....	68
11.6.1	Data Collection	68
11.6.2	Source Documentation.....	68
11.6.3	Archives	68
11.7	Insurance	68
11.8	Publication Policy.....	69
11.9	Investigator and Administrative Structure	70
12.	LITERATURE REFERENCE LIST.....	71
13.	SUMMARY OF CHANGES	72
14.	APPENDICES	73

CCI

Appendix 7 Focused Physical Examination Form Example.....	83
--	-----------

 EST. 1981	<small>Title</small> 43QM2106 Clinical Study Protocol – QM1114 – GL	<small>Doc id</small> MA-49290
---	---	--

[figure not shown]
Appendix 8 Adverse Events Potentially Suggestive of Remote Spread of Toxin.....	85
SIGNED AGREEMENT OF THE CLINICAL STUDY PROTOCOL (CSP)	86

List of Tables

Table 1	Clinical Study Schematic.....	16
Table 2	Schedule of Assessments	18
Table 3	Description and Usage of the Study Products(s)	38

List of Figures

Figure 1	Study Flow Chart	17
Figure 2	Injection Sites for Treating Glabellar Lines.....	40

GALDERMA EST. 1981	Title 43QM2106 Clinical Study Protocol – QM1114 – GL	Doc id MA-49290
SYNOPSIS		

Clinical Study Title: A Phase 3b, Randomized, Double-Blind, Placebo-Controlled Study to Assess Aesthetic Improvement and Onset of QM1114-DP Treatment Effect in Subjects with Moderate to Severe Glabellar Lines
		

Short Title: The RELAX study (RELabotulinumtoxin Assessment of eXtended duration)
		
Clinical Study Population:	Male and female subjects, 18 years of age and older with moderate to severe glabellar lines (GL) at maximum frown.	
Clinical Study Design:	
This is a multi-center, randomized, double-blind, placebo-controlled study to assessed aesthetic improvement and onset of QM1114-DP treatment effect in subjects with moderate to severe GL.
 
Following the informed consent and screening process, eligible subjects will be randomly assigned in a 3:1 ratio to receive a single treatment at baseline (Day 0) of 50 units (U) of QM1114-DP (90 subjects) or placebo (30 subjects) in the glabellar region.
 
Following treatment at baseline, subjects will be monitored for safety and efficacy according to the Schedule of Assessments for 12 months.
	
Target Indication:	Glabellar lines	
Total Number of Subjects (Planned):	Approximately 120 subjects.	
Number of Clinical Study Centers (Planned):	Up to 5 study centers.	
Region(s) / Country(ies) Involved (Planned):	United States (US)	
Clinical Study Duration:	
The planned duration of recruitment (i.e. from First Subject First Visit [FSFV] to Last Subject First Visit [LSFV]) is approximately 2 months.
 
The planned clinical study duration (i.e. from FSFV to Last Subject Last Visit [LSLV]) is approximately 14.5 months.
	
Duration of Subject Participation:	Clinical study participation for each subject is up to 12.5 months.	
Key Inclusion Criteria:	
1. Male or female, 18 years of age or older.
 
C  C  I 
 
4. Previous repeated treatments with BoNT-A products for aesthetic use within 3 years prior to the screening visit.
 
5. Female of non-childbearing potential (i.e., post-menopausal [absence of menstrual bleeding for 1 year prior to screening, without any other medical reason], or has undergone hysterectomy or bilateral oophorectomy).
 
OR
 
6. Female of childbearing potential with a negative urine pregnancy test at screening and baseline, and agrees to use a highly effective and approved contraceptive method for the duration of the study. A highly effective method of contraception is defined as:
	

CONFIDENTIAL

Page 9 of 86

Effective date: 2022-03-21 13:08

Effective

Version: 3.0

GALDERMA
EST. 1981Title
43QM2106 Clinical Study Protocol – QM1114 – GLDoc id
MA-49290

SYNOPSIS	
	
 • Bilateral tubal ligation; • Combined (estrogen and progesterone containing) oral, intravaginal or transdermal contraceptives that inhibit ovulation as the primary mode of action, on a stable dose for at least 28 days prior to screening visit; • Intrauterine device (IUD) inserted at least 28 days prior to screening visit; • Intrauterine hormone-releasing system; • Partner vasectomized for at least three months prior to screening visit; • Progestogen-only oral, injectable or implantable contraceptives that inhibit ovulation as the primary mode of action, on a stable dose for at least 28 days prior to screening visit; or • Strict abstinence (i.e., refraining from heterosexual intercourse for the duration of the subject's participation in the study). 
7. Time and ability to complete the study and comply with instructions.
 
8. Understands the study requirements and signed the informed consent form (ICF).

Key Exclusion Criteria:	
 1. Previous use of any botulinum toxin in facial areas within 9 months prior to study treatment. 2. Anticipated need for treatment with botulinum toxin of any serotype for any reason during the study (other than the investigational product). 3. Female who is pregnant, breast feeding, or intends to conceive a child during the study. 4. Known allergy or hypersensitivity to any component of the investigational product (QM1114-DP) or any botulinum toxin serotype. 5. Inability to substantially lessen GL by physically spreading them apart, as determined by the investigator. 6. Clinically significant abnormal focused physical exam finding(s) at screening or baseline visits, in the investigator's opinion. 7. Excessive skin laxity in the treatment area or periorbital area. 8. Previous use of any hyaluronic acid soft tissue augmentation therapy in the glabella area within 6 months before baseline. 9. Previous soft tissue augmentation with any permanent (non-biodegradable such as silicone, polyacrylamide, etc.) or semi-permanent (i.e., calcium hydroxylapatite, poly-L-Lactic acid or polymethyl-methacrylate) product; lifting threads, or autologous fat in the treatment area. 10. History, presence, or predisposition of eyelid or eyebrow ptosis (heavy eyebrows), amblyopia (i.e., lazy eye), or previous surgery around the eye that may lead to the above events, as determined by the investigator. 11. Marked facial asymmetry, excessive dermatochalasis (i.e., excess of skin in eyelids), or marked periocular or eyebrow asymmetry. 12. Presence of scar(s), piercing(s), or tattoo(s) (including microblading of eyebrow or eyeliner) in the treatment area or around the treatment area that, in the investigator's opinion, may interfere with study evaluations. 13. Presence of inflammation, active infection or skin disorder, such as

[figure not shown]
CONFIDENTIAL

Page 10 of 86

	
Title 43QM2106 Clinical Study Protocol – QM1114 – GL
	
Doc id MA-49290

--	--	-----------------------------------

SYNOPSIS	
	
eczema, rosacea, facial psoriasis, herpes zoster etc., near or in the treatment area.
 
14. Presence of cancerous or pre-cancerous lesions in the treatment area.
 
15. History of other facial treatment, surgery or other aesthetic procedures (e.g. ablative skin resurfacing, laser treatment, micro needling, chemical peel) in the previous 12 months that, in the investigator's opinion, could interfere with study injections and/or assessments or expose the subject to undue risk by study participation.
 
16. Planned facial surgery, eye surgery (including LASIK procedure) or aesthetic procedures (e.g. ablative skin resurfacing, laser treatment, micro needling, chemical peel, botulinum toxin treatment, or dermal fillers) in the face during the study period.
 
17. History or presence of facial nerve palsy, or any medical condition that may put the subject at increased risk with exposure to botulinum toxin including diagnosed myasthenia gravis, Lambert-Eaton syndrome, amyotrophic lateral sclerosis, or any other condition that might interfere with neuromuscular function.
 
18. Use of medications that affect neuromuscular transmission such as curare-like depolarizing agents, lincosamides, polymyxins, anticholinesterases, and aminoglycoside antibiotics.
 
19. Subject with bleeding disorder or subject currently using anticoagulants.
 
20. Subject has any prior or current psychiatric illness (e.g. Psychosis, depression, anxiety), alcohol or drug abuse, or is taking antidepressant, anxiolytic, or antipsychotic medication that, in the investigator's opinion, could affect the subject's safety and/or participation in the study.
 
21. Other concurrent medical conditions, therapy, or other condition that, in the investigator's opinion, would interfere with the evaluation of the study medication, safety or efficacy, and/or put the subject at risk if he/she participates to the study.
 
22. Participation in an investigational device or drug study within 30 days prior to study treatment or plans to enroll in any other investigational study during participation in this study.
 
23. Study center personnel, close relatives of the study center personnel (e.g. parents, children, siblings, or spouse), employees or close relatives of employees at the sponsor company.


Investigational Product:
 
Strength/Concentration:
 
Dosage (total daily dose):
 
Route:
 
Dose regimen:
 
Location of treated area:
	
QM1114-DP is a BoNT-A, supplied as a sterile, buffered solution for injection containing the drug substance (QM1114-DS).
 
100 U/ml
 
50 U total (0.5 mL)
 
10 U per injection point (0.1 mL per injection point)
 
Intramuscular injection
 
Single treatment at baseline visit
 
Glabellar region

 EST. 1981	Title 43QM2106 Clinical Study Protocol – QM1114 – GL	Doc id MA-49290
---	--	---------------------------

SYNOPSIS	
Placebo Product:	The matching placebo for QM1114-DP is supplied as a sterile, buffered solution for injection, containing the excipients for the investigational product but without the drug substance (QM1114-DS).
Strength/Concentration:	N/A
Dosage (total daily dose):	0.5 mL total, 0.1 mL per injection point
Route:	Intramuscular injection
Dose regimen:	Single treatment at baseline visit
Location of treated area:	Glabellar region
Efficacy Assessments:	
 • 7-point Global Aesthetic Improvement Scale (GAIS) (subject assessment) • Diary Card (subject assessment) CC1 
Study Objective:	The objectives of the study are to evaluate the aesthetic improvement and onset of QM1114-DP treatment effect in subjects with moderate to severe glabellar lines.
Primary Efficacy Objective and Endpoint:	
1. To demonstrate superiority in aesthetic improvement following a single dose of QM1114-DP compared to placebo as assessed by the subject using the GAIS at maximum frown at Month 1.
 
Endpoint: Responder rate based on the 7-point GAIS. A responder is defined as a subject who responds at least "Improved" on the GAIS at maximum frown.

Secondary Efficacy Objectives and Endpoints:	
1. To evaluate onset of treatment effect following a single dose of QM1114-DP and placebo as assessed by the subject using the diary card on Days 0 through 7 post-treatment.
 
Endpoint: Onset of effect is defined as the first day a subject answers "yes" to the diary question.
 
2. To evaluate aesthetic improvement following a single dose of QM1114-DP and placebo as assessed by the subject using the GAIS at maximum frown at all applicable post-treatment time points.
 
Endpoint: Responder rate based on the 7-point GAIS. A responder is defined as a subject who responds at least "Improved" on the GAIS at maximum frown.

CONFIDENTIAL

Page 12 of 86

Effective

Effective date: 2022-03-21 13:08

Version: 3.0

SYNOPSIS

CCI

Effective date: 2022-03-21 13:08

Effective

Version: 3.0

GALDERMA EST. 1981	Title 43QM2106 Clinical Study Protocol – QM1114 – GL	Doc id MA-49290
	
SYNOPSIS
 
CCI
 
CCI [REDACTED]
	
Safety Assessment:	
 • Adverse Events (AEs) • Focused Physical Examination (FPE) • Vital Signs • Production of neutralizing antibodies against QM1114-DP 	
Safety Objectives and Endpoints:	
To evaluate the safety of a single dose of 50U of QM1114-DP and placebo in the treatment of moderate to severe GL.
 
Endpoints:
 
 • Incidence and severity of treatment emergent AEs (TEAEs) • FPE findings • Vital signs • Neutralizing antibody production 	
Other Assessments:	
 • Photography • Pregnancy Test 	
Blinding:	
This is a double-blind study in which neither the investigator, sub-investigator, study staff, nor the subject will know the subject's study product assignment (i.e., QM1114-DP or placebo). Placebo is identical in appearance to QM1114-DP but contains no active drug substance.
 
Subjects will be randomized at baseline to either treatment with QM1114-DP or placebo. In order to maintain the blind, the study products, QM1114-DP and placebo, will be supplied in identical vials, each with a unique number on the vial label. Both QM1114-DP and placebo will be administered in exactly the same way.
	
Principal Statistical Method:	
Analysis populations:
 
 • The intention-to-treat (ITT) population includes all subjects who are 	

CONFIDENTIAL

Page 14 of 86

Effective date: 2022-03-21 13:08

[figure not shown]
Effective

Version: 3.0

SYNOPSIS	
	
randomized and dispensed the investigational product, and will be analyzed according to the randomization scheme. The ITT population will be the primary population used for efficacy analysis.
 
 • The per protocol (PP) population is a subset of the ITT subjects who complete the Month 1 visit and have no protocol deviations that are considered to have a substantial impact on the primary efficacy outcome. • The safety population includes all subjects who were administered the study product, and will be analyzed according to as-treated principle. All safety data will be summarized descriptively based on the safety population. 
CCI

Sample Size:	
Interim Analysis:	Not applicable.

2022-03-21 13:08

[figure not shown]
Effective date:

CLINICAL STUDY SCHEMATIC AND FLOW CHART**Table 1 Clinical Study Schematic***Effective*

Version: 3.0

2022-03-21 13:08

Effective date:

Figure 1 Study Flow Chart**Effective**

Version: 3.0

GALDERMA EST. 1981	Title 43QM2106 Clinical Study Protocol – QM1114 – GL	Doc id MA-49290
------------------------------	--	---------------------------

SCHEDULE OF ASSESSMENTS

Table 2 Schedule of Assessments

Visit	Visit 1	Visit 2	Visit 3	Visit 4	Visit 5	Visit 6	Visit 7	Visit 8	Visit 9	Visits 10-14	Visit 15
1 month = 4 weeks All visit windows are calculated from Baseline/Day 0		Day 0 Baseline ¹	Day 1	Day 2	Day 3	Day 4	Month 1	Month 3	Month 6	Months 7-11	Month 12/ EOS/ET ²
Window	(≤ 2 weeks of Visit 2)						(± 5 days)	(± 5 days)	(± 5 days)	(± 5 days)	(± 5 days)
Informed Consent	X										
Demographic Data ³	X										
Medical History	X										
Previous Medication/Procedures ⁴	X										
Urine Pregnancy Test ⁵	X	X ⁷									X
Focused Physical Examination ⁶	X	X ⁷	X	X	X	X	X	X	X	X	X
Vital Signs ⁸	X	X ¹⁰	X	X	X	X	X	X	X	X	X
Inclusion/Exclusion Criteria	X	X ⁷									
Photography		X ⁷	X	X	X	X	X	X	X	X	X
CCI											
Blood sample for serum antibody testing		X ⁷					X		X		
Randomization		X ⁷									
Treatment		X									
Dispense Subject Diary Card		X									
Collect Subject Diary Card							X				
Adverse Events	X	X ¹⁰	X	X	X	X	X	X	X	X	X
Concomitant Medication/Procedures	X	X ¹⁰	X	X	X	X	X	X	X	X	X
SUBJECT ASSESSMENTS											
CCI											
GAIS			X	X	X	X	X	X	X	X	X
INVESTIGATOR ASSESSEMENTS											
CCI											

CONFIDENTIAL
Page 18 of 86

GALDERMA EST. 1981	Title 43QM2106 Clinical Study Protocol – QM1114 – GL	Doc id MA-49290
------------------------------	--	---------------------------

Visit	Visit 1	Visit 2	Visit 3	Visit 4	Visit 5	Visit 6	Visit 7	Visit 8	Visit 9	Visits 10-14	Visit 15
1 month = 4 weeks All visit windows are calculated from Baseline/Day 0		Day 0 Baseline ¹	Day 1	Day 2	Day 3	Day 4	Month 1	Month 3	Month 6	Months 7-11	Month 12/ EOS/ET ²
Window	(≤ 2 weeks of Visit 2)						(± 5 days)	(± 5 days)	(± 5 days)	(± 5 days)	(± 5 days)
CCI											

Abbreviations:EOS = End of Study; ET = Early Termination; **CCI**GAIS = Global Aesthetic Improvement Scale; **CCI**

1. Screening and baseline visits may be performed on the same day. If performed on the same day, study activities should only be completed once (i.e., UPT, subject and investigator GL severity assessments, focused physical exam, vital signs, and inclusion/exclusion criteria review).
2. If the subject withdraws before the final visit the assessments at Month 12/EOS/ET should be completed, if possible.
3. Includes date of birth, gender, race, ethnicity, height, weight, Fitzpatrick skin type.
4. For previous toxin treatments, capture; brand, area(s) treated, and date(s) on the previous medications/procedures form.
5. Females of childbearing potential.
6. Post-baseline, events suggestive of remote spread of toxin are also considered while doing clinical evaluations based on the subject's symptoms and signs. Directed questioning and examination will then be performed as appropriate.
7. Performed pre-treatment.
8. Vital signs include blood pressure, heart rate and respiratory rate. Vital signs are taken seated, after approximately 10 min rest.
9. Only at select sites.
10. Performed pre- and post-treatment.
11. Subject will make his/her assessment independently of the investigator's assessment.
12. Performed at month 9 only
13. Part 1 to be completed post-treatment at baseline (Visit 2) and Part 2 to be completed at Month 1 (Visit 7).

CONFIDENTIAL
Page 19 of 86

GALDERMA <small>EST. 1981</small>	Title 43QM2106 Clinical Study Protocol – QM1114 – GL	Doc id MA-49290
---	---	----------------------------------

LIST OF ABBREVIATIONS AND DEFINITIONS OF TERMS

Abbreviation/Term	Definition
°C	Degrees Celsius
AE	Adverse event
BCOP	Bovine corneal opacity and permeability
BOCF	Baseline observation carried forward
BoNT	Botulinum toxin
BoNT-A	Botulinum toxin type A
CFR	Code of Federal Regulations
CM	Centimeter
CMH	Cochran Mantel Haenszel
CRO	Contract research organization
CSP	Clinical study protocol
CSR	Clinical study report
CTA	Clinical trial agreement
CTN	Clinical trial number
DMP	Data management plan
eCRF	Electronic case report form
EDC	Electronic data capture
e.g.	For Example (Latin: exempli gratia)
EOS	End of study
ET	Early termination
EU	European Union
°F	Degrees Fahrenheit
FDA	Food and Drug Administration
FL	Forehead lines
CCI	
FPE	Focused Physical Examination
FSFV	First Subject First Visit (first subject screened, i.e. who signs the informed consent form)
GAIS	Global Aesthetic Improvement Scale
GCP	Good Clinical Practice
GL	Glabellar lines
CCI	

Effective date: 2022-03-21 13:08

Effective

Version: 3.0

Abbreviation/Term	Definition
CCI	[REDACTED]
GLP	Good Laboratory Practices
HIPAA	Health Insurance Portability and Accountability Act of 1996
IB	Investigator's brochure
ICF	Informed consent form
ICH	International Council for Harmonisation
i.e.	That is (Latin: id est)
ILA	Investigator Live Assessment
IM	Intramuscular
IND	Investigational New Drug
Investigator	The principal investigator (PI) or other qualified person, i.e. sub-investigator, designated and supervised by the PI at a study site to perform critical study-related procedures or to make important study-related decisions as specified on the signature and delegation log
Investigator File	Essential documents relating to a clinical study as defined in applicable GCP guidance document and maintained by the investigator.
Investigational Product	A pharmaceutical form of an active ingredient being tested in a clinical study, including a product with a marketing authorization when used or assembled (formulated or packaged) in a way different from the approved form, or when used for an unapproved indication, or when used to gain further information about an approved use.
IRB	Institutional review board
ITT	Intention-to-treat
IUD	Intrauterine device
kDa	Kilodalton
LCL	Lateral canthal lines
LSFV	Last subject first visit (last subject screened, i.e. who signs the informed consent form)
LSLV	Last subject last visit (last subject who completed its last clinical study visit)
MAS	Merz Aesthetics Scale™
MD	Medical Doctor
MedDRA	Medical Dictionary for Regulatory Activities
MI	Multiple imputation

CONFIDENTIAL

Page 21 of 86

 EST. 1981	Title 43QM2106 Clinical Study Protocol – QM1114 – GL	Doc id MA-49290
	Abbreviation/Term	Definition
Mg	Milligram	
mL	Milliliter	
mM	Millimoles	
MTD	Maximum tolerated dose	
N or n	Number	
N/A	Not applicable	
OC	Observed cases	
OTC	Over-the-counter	
PI	Principal investigator; qualified person responsible for conducting the study at a study site	
PP	Per-protocol	
PQC	Product quality complaint	
PT	Preferred term	
QA	Quality assurance	
RA	Regulatory authority	
Reference product	An investigational or marketed product (i.e. active control), or placebo, used as a comparator in a clinical study	
SAE	Serious adverse event	
SAP	Statistical analysis plan	
SIN	Subject identification number	
SOC	System organ class	
SOP	Standard operating procedure	
Sponsor File	Essential documents relating to a clinical study as defined in applicable GCP guidance document and maintained by the sponsor.	
SLA	Subject Live Assessment	
Study Files	The investigator file and the sponsor file	
Study Products	The investigational product and the reference product under study	
Study Site	The location(s) where the study-related activities are actually conducted	
SUSAR	Suspected unexpected serious adverse reactions	
TEAE	Treatment emergent adverse event	
U	Unit	
UPT	Urine pregnancy test	
US	United States	

Effective date: 2022-03-21 13:08

Effective date:

Effective

Version: 3.0

Abbreviation/Term	Definition
v/v	Volume/volume
WFI	Water for injection
WHO	World Health Organization

 EST. 1981	Title 43QM2106 Clinical Study Protocol – QM1114 – GL	Doc id MA-49290
---	--	---------------------------

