3. OVERALL CLINICAL STUDY DESCRIPTION

This is a multi-center, randomized, double-blind, placebo-controlled study to assessed aesthetic improvement and onset of QM1114-DP treatment effect in subjects with moderate to severe GL.

Following the informed consent and screening process, eligible subjects will be randomly assigned in a 3:1 ratio to receive a single treatment at baseline (Day 0) of 50 U of QM1114-DP (90 subjects) or placebo (30 subjects) in the glabellar region.

Following treatment at baseline, subjects will be monitored for safety and efficacy according to the Schedule of Assessments for 12 months.

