5.4.5 Prohibited Concomitant Therapies

The following therapies are prohibited because they may interfere with the efficacy and/or safety assessment of the study products(s):

- Botulinum toxin of any serotype.
- Any other investigational new drug or device.

CONFIDENTIAL

Page 35 of 86

 EST. 1981	Title 43QM2106 Clinical Study Protocol – QM1114 – GL	Doc id MA-49290
---	--	---------------------------

- Any absorbable (temporary) or non-absorbable (permanent) material in the treatment area.
- Facial aesthetic procedures (e.g., ablative skin resurfacing, laser treatment, micro needling, photodynamic therapy, tattooing or chemical peel) or any other procedures in the treatment area.
- Facial surgery or eye surgery (including LASIK procedure).
- Medications that affect neuromuscular transmission such as curare-like depolarizing agents, lincosamides, polymyxins, anticholinesterases and aminoglycoside antibiotics.

If a prohibited therapy becomes a necessary treatment for best clinical interest of the subject or due to safety reason, the Medical Monitor (Section 11.9) should be notified, if time permits, to discuss possible alternatives prior to administration of a prohibited therapy.

If a subject receives a prohibited therapy during the clinical study, the Medical Monitor (Section 11.9) should be notified to discuss the subject's continuation in the clinical study.

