1.5.1 Adverse events

Adverse events (AEs) are to be monitored throughout the course of the study. All AEs reported will be coded using the Medical Dictionary for Regulatory Activities (MedDRA, Version 25.0 – March 2022 or higher) and classified by MedDRA preferred term (PT) and system organ class (SOC). AEs will be defined as treatment-emergent adverse events (TEAEs) if the AE had an onset time greater than or equal to the time of study treatment. The study period for the purpose of AE collection is defined as the period from the signing of a study specific informed consent to study exit.

A two-point scale (“Yes” or “No” response) will be used for the causality assessments. The Treating Investigator should be asked to indicate a response to each of the following questions in the electronic Case Report Form (eCRF):

- “Do you consider that there is a reasonable possibility that the event may have been caused by the study product?”
- “Do you consider that there is a reasonable possibility that the event may have been caused by the study product injection procedure?”

If either of these questions is answered with a ‘Yes’, the AE will be considered related.

All AEs will be monitored by the Sponsor to determine if they meet the criteria of remote spread of effect of the toxin or hypersensitivity, which will be included as an AE endpoint. A list of preferred terms for these types of events will be analyzed to determine if there is a plausible possibility that they represent remote spread of toxin or hypersensitivity. The Sponsor will consider variables including alternative etiology (medical history, concomitant medications, or diagnosis which could account for the symptoms), location of QM1114-DP administration, and temporal relationship to

QM1114-DP administration in order to perform the analysis. Sponsor determination will be cross-referenced with Investigator-reported potential remote spread of the toxin or hypersensitivity AEs. Before unblinding the subject data, and as a part of preparations for the database lock, the study team will review and adjudicate all AEs to create a finalized list of remote spread of toxin or toxin hypersensitivity events for the analysis.

Refer to Galderma Work Instruction QMS-13549 effective 16MAR2022 and to the Data Management Plan V1.0 for more details on this process.

AE endpoints include incidence and severity of TEAEs.

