2.2 Analysis Populations

The statistical analyses will be performed based on the following three subject populations:

- Intention-to-treat Population - The Intent-to-treat (ITT) population includes all subjects who are randomized and dispensed the investigational product and will be analyzed according to the randomization scheme.

- Per-protocol Population - The Per-protocol (PP) population includes the ITT subjects who complete the Month 1 visit and have no protocol deviations that are considered to have a substantial impact on the primary efficacy outcome.
- Safety Population - The safety population includes all subjects who were administered the study product and will be analyzed according to as-treated principle.

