2.5.2 Adverse events

All AE data will be summarized by treatment group. Missing dates will be imputed as described below. AEs will be summarized by SOC and PT. AEs occurring before treatment will be presented in listings only. The MedDRA version used for the coding will be noted as a footnote in the tables and listings. In general, percentages for the number of subjects will be calculated using the number of subjects in the safety population for the denominator.

A summary of all AEs will be provided, which will include:

- number (%) of subjects who did not have an AE
- number (%) of subjects with at least one TEAE and number of events
- number (%) of subjects and events with at least one TEAE related to study product or injection procedure and number of events
- number (%) of subjects and events with at least one TEAE not related to study product or injection procedure and number of events
- number (%) of subjects and events with at least one TEAE leading to discontinuation and number of events
- number (%) of subjects and events with at least one serious TEAE and number of events
- number (%) of subjects and events with at least one serious related TEAE and number of events
- number (%) of subjects and events with at least one AE that meets the criteria of remote spread of effect of toxin or hypersensitivity and number of events

Summaries of TEAEs (including the total number of events, number and percentage of subjects) will be displayed by treatment group according to the following:

- All TEAEs by SOC and PT
- Treatment emergent SAE by SOC, PT, maximum intensity (mild, moderate, severe), and causality
- Related TEAEs by SOC and PT, and maximum intensity (mild, moderate, severe)
- Unrelated TEAEs by SOC and PT, and maximum intensity (mild, moderate, severe)
- TEAEs leading to discontinuation by SOC and PT, and maximum intensity (mild, moderate, severe)
- TEAEs by SOC, PT, and action taken (none, medical treatment, non-pharmacological treatment, subject withdrawn)
- TEAEs that meet the criteria of remote spread of effect of toxin or hypersensitivity by SOC, PT, and maximum intensity (See [Section 2.5.2.2](#))

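### TEAE incidence is a crude percentage of everyone dosed with no summary of follow-up time, so it would mislead if one arm left the 48-week study earlier

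*Protocol*

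**What the plan says.** The Protocol synopsis (Clinical Study Design) states that after treatment "subjects will be monitored for safety and efficacy according to the Schedule of Assessments for 12 months". The Schedule of Assessments sets "1 month = 4 weeks". Section 3 allocates "50 U of QM1114-DP (90 subjects) or placebo (30 subjects) in the glabellar region".

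On collection of adverse events, SAP 1.5.1 says: "The study period for the purpose of AE collection is defined as the period from the signing of a study specific informed consent to study" (the sentence closes with the subject's exit as the end point). On the denominator, SAP 2.5.2 says that in general "percentages for the number of subjects will be calculated using the number of subjects in the safety population for the denominator", and SAP 2.2 defines that population: "The safety population includes all subjects who were administered the study product and will be analyzed according to as-treated principle". Each dosed subject therefore counts once in the denominator, however long he or she was observed.

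Three other provisions come close but do not bring in time at risk:
- SAP 2.5.1 (extent of exposure) reports how many subjects were dosed and the injection characteristics, not the length of follow-up.
- SAP 2.5.2 summarises time to onset and duration, but only for related TEAEs and per event, so there is no at-risk denominator.
- Protocol 9.1.3 plans Kaplan-Meier methods for onset and duration of treatment response, not for adverse events.

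No readable section plans a subject-time summary, an exposure-adjusted rate, a fixed-window incidence or a time-to-first-TEAE analysis.

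On the population, inclusion criterion 4 requires "Previous repeated treatments with BoNT-A products for aesthetic use within 3 years prior to the screening visit", and Protocol 5.4.5 lists "Botulinum toxin of any serotype" among the prohibited therapies.

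**The concern.** A crude percentage compares two arms fairly only if both are observed for about the same time. A subject who leaves at Month 2 has a short period in which a TEAE can be recorded, yet weighs as much in the denominator as a subject followed for 48 weeks. If follow-up differs by arm, the percentages differ even when the true risk is the same.

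Unequal follow-up is foreseeable here. Subjects are repeat toxin users, toxin is barred during the study, Protocol 1.3 anticipates no benefit in the placebo group, and Protocol 5.5 lets any subject leave at any time. A placebo subject who sees no effect has a reason to go. That would lower the placebo percentage and make QM1114-DP look worse than it is. If active subjects left earlier instead, the same mechanism would hide harm.

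Incidence of TEAEs is the first safety endpoint listed in Protocol 2.1.4, so the figure will be read as a main safety result. Because the table is descriptive, no test or interval would warn the reader of such a shift.

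**Working it through.** The documents give no TEAE rate and no dropout rate, overall or by arm, so there is no stated figure to reproduce. The calculation below shows scale only.

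**Inputs from the documents.** Follow-up T = 12 × 4 = 48 weeks; 90 active and 30 placebo subjects.

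**Assumptions.** The TEAE hazard is constant and equal in both arms, so there is no true difference. The true 48-week risk p is 10%, 30% or 50%. Dropout is exponential, unrelated to AE risk, starts at week 4 and reaches a proportion d by week 48.

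**Formulas.**
- TEAE hazard per week: l = −ln(1 − p)/48
- Dropout hazard per week: m = −ln(1 − d)/44
- Expected crude incidence: 1 − exp(−4l) + exp(−4l) × [l/(l + m)] × [1 − exp(−44(l + m))]
- Mean follow-up in weeks: 4 + [1 − exp(−44m)]/m

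**Worked case: p = 30%, dropout 10% active and 30% placebo.**
- l = 0.3567/48 = 0.00743. The first four weeks contribute 1 − exp(−0.0297) = 0.0293 in each arm.
- Active: m = 0.1054/44 = 0.00239; crude incidence = 0.0293 + 0.9707 × 0.7563 × 0.3510 = 28.7%; mean follow-up 45.8 weeks.
- Placebo: m = 0.3567/44 = 0.00811; crude incidence = 0.0293 + 0.9707 × 0.4783 × 0.4952 = 25.9%; mean follow-up 41.0 weeks.
- Spurious difference (active minus placebo): +2.8 points.
- Standard error: √(0.287 × 0.713/90 + 0.259 × 0.741/30) = 9.3 points. One placebo subject is 1/30 = 3.3 points.

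**Range of spurious differences, in percentage points (active minus placebo).**

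| Assumed dropout, active/placebo | True risk 10% | True risk 30% | True risk 50% |
|---|---|---|---|
| 10%/10% | 0 | 0 | 0 |
| 5%/20% | +0.7 | +2.0 | +3.1 |
| 10%/30% | +1.0 | +2.8 | +4.3 |
| 10%/40% | +1.5 | +4.3 | +6.7 |
| 10%/50% | +2.0 | +5.9 | +9.2 |

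Reversing the dropout (30% active, 10% placebo) at 30% risk gives −2.8 points. Every value in the table is below one standard error of the difference; the closest is 9.2 points against 10.3.

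**Harsher assumptions.** Suppose all placebo leavers go between Months 1 and 6 and the first-TEAE rate is 1.0 per subject-year (60.1% of completers affected). Dropout of 30% on placebo, against 10% on active spread over Months 1 to 12, then gives 57.9% versus 49.0%, a gap of 8.9 points. A gap of 18.8 points needs 50% placebo dropout in that window and 1.5 first TEAEs per subject-year, which means about 75% of completers with a TEAE.

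**With the fix.** Under the same assumptions, a Kaplan-Meier estimate at 48 weeks has expectation 30% in both arms at p = 30%. The first-event rate is 0.00743 × 5,200 = 38.6 per 100 subject-years (52-week years) in both arms. The spurious difference is zero.

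**The case against.** A reader might infer that the placebo TEAE rate will be understated and that the safety comparison is therefore biased. The documents do not support that as a statement of fact. It needs earlier placebo exit, which they neither report nor assume, and several provisions work against it:
- Anticipated need for toxin, and planned facial toxin or aesthetic procedures, are exclusions (5.2.2, criteria 2 and 16).
- Entrants have already gone nine months without facial toxin (criterion 1) and must have the time and ability to complete the study (5.2.1, criterion 6).
- Receiving a prohibited therapy leads to a discussion with the Medical Monitor, not automatic exit (5.4.5).
- Protocol 1.1 puts the usual class effect at about 4 to 6 months, so active subjects may also have reason to leave before Month 12.

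Nor should Protocol 1.3 be read as showing that placebo subjects are told to expect nothing. It is a risk/benefit statement about the group. The trial is double-blind (6.4), and subjects can only infer their arm from what they see.

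The reach of the problem is also limited. Treatment is a single injection, and events in the first month are barely affected if dropout begins after that. Related and unrelated TEAEs are tabulated separately, so the distortion falls mainly on later, unrelated events. Safety is descriptive (SAP 2.5), so no test or error rate is at stake. Disposition by visit and arm (Protocol 9.1.3) would reveal unequal exit, and leavers have an exit assessment where possible (5.5).

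All of this stands, and it sets the priority. It does not close the gap: a disposition table can show unequal follow-up but cannot correct the percentages, and the provisions above make differential exit less likely without ruling it out.

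**Conclusion.** The point holds in conditional form. SAP 2.5.2 uses a crude denominator, adverse events stop being collected at exit, and no readable analysis accounts for time at risk. If one arm leaves earlier, its TEAE percentage would be understated. Earlier placebo exit is plausible but undocumented, and the direction could be nil or reversed.

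On the assumptions shown, the spurious difference is zero with equal dropout, about 1 to 4 points with moderately unequal dropout (5%/20% or 10%/30%), and about 9 points at 10%/50% with a true risk of 50%. Larger values need more extreme assumptions. With 30 placebo subjects the shift is below one standard error throughout the main table, but it is systematic. Priority: minor.

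**What to change.** Change SAP 2.5.1 and 2.5.2 before unblinding, as follows:
- Keep the crude percentages as planned.
- In 2.5.1, add the subject-time at risk by arm, from injection to study exit.
- In 2.5.2, add the Kaplan-Meier cumulative incidence of the first TEAE by arm at Months 1, 6 and 12 (weeks 4, 24 and 48), for any, related and serious TEAEs, censoring subjects without an event at study exit.
- State that where follow-up differs by arm, any descriptive comparison of TEAE incidence rests on these figures.

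The cost is SAP wording and one extra table from data already collected, plus a second set of incidence figures to explain. The estimate is valid if exit is unrelated to AE risk, and the SAP should say so. If follow-up turns out equal, the addition leaves the comparison between arms unchanged.
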